13.2 Pregnancy

Due to the study enrollment criteria and proposed population, women of child bearing potential (as defined in Section 4.2) are excluded from participation in this study. In the unlikely event that pregnancy should occur during the course of the study, all outcomes of pregnancy should be reported to the ARC.

15. APPENDIX A – DEFINITIONS FOR STUDY ENDPOINTS

15.1 Bleeding events

15.1.1 Bleeding Academic Research Consortium definition of bleeding

Clinically relevant bleeding is defined as any bleeding event that meets the BARC criteria types 2, 3 or 5.

Table 4 BARC Bleeding Definition, modified from Mehran et al (26)

Type	Definition
0	No evidence of bleeding.
1	Bleeding that is not actionable and patient does not have unscheduled studies, hospitalization or treatment by a health care professional
2	Any clinically overt sign of hemorrhage that is actionable but does not meet criteria for type 3, 4 or 5 bleeding. It must meet at least one of the following criteria: 
 requiring medical or percutaneous intervention guided by a health care profession, includes (but are not limited to) temporary/permanent cessation of a medication, coiling, compression, local injection leading to hospitalization or an increased level of care prompting evaluation defined as an unscheduled visit to a healthcare professional resulting in diagnostic testing (laboratory or imaging)
3	Clinical, laboratory and/or imaging evidence of bleeding with specific healthcare provider responses, as listed below:
3a	
 Any transfusion with overt bleeding Overt bleeding plus hemoglobin (Hb) drop ≥ 3 to < 5g/dL* (provided Hb drop is related to bleeding)
3b	
 Overt bleeding plus Hb drop ≥ 5g/dL* (Hb drop is related to bleed) Cardiac tamponade Bleeding requiring surgical intervention for control (excluding dental/nasal/skin/hemorrhoid) Bleeding requiring intravenous vasoactive drugs
3c	
 Intracranial hemorrhage (does not include microbleeds or hemorrhagic transformation; does include intraspinal). Subcategories: confirmed by autopsy, imaging or lumbar puncture

* Hemoglobin drop should be corrected for for intracurrent transfusion in which 1 unit of packed red blood cells or whole blood should be expected to increase hemoglobin by 1g/dL.

Type	Definition
	
 Intraocular bleed compromising vision
4	CABG – Related Bleeding 
 Perioperative intracranial bleeding within 48 hours Reoperation following closure of sternotomy for the purpose of controlling bleeding Transfusion of ≥ 5 units of whole blood or packed red blood cells within a 48 hour period Chest tube output $\geq 2L$ within a 24 hour period
5	Fatal Bleeding. Bleeding directly causes death with no other explainable cause. Categorized further as either definite or probable.
5a	Probable fatal bleeding is bleeding that is clinically suspicious as the cause of death, but the bleeding is not directly observed and there is no autopsy or confirmatory imaging.
5b	Definite fatal bleeding is bleeding that is directly observed (either by clinical specimen – blood, emesis, stool, etc. – or by imaging) or confirmed on autopsy.

15.1.2 Thrombolysis in Myocardial Infarction definition of bleeding

Table 5 TIMI Bleeding Definition(27)

Type	Definition
Non-CABG related bleeding	
Major	
 Any intracranial bleeding (excluding microhemorrhages < 10 mm evident only on gradient-echo MRI) Clinically overt signs of hemorrhage associated with a drop in hemoglobin of ≥ 5 g/dL or a $\geq 15\%$ absolute decrease in haematocrit Fatal bleeding (bleeding that directly results in death within 7 days) 
Life threatening bleeding is a TIMI major bleeding event that meets any of the following criteria:
 
 Symptomatic intracranial hemorrhage Fatal bleeding Leads to hypotension requiring inotropic agents Requires surgical intervention for ongoing bleeding Necessitates transfusion of 4 or more units of whole blood or packed red blood cells over a 48-hour period

Type	Definition
Minor	
 • Clinically overt (including imaging), resulting in hemoglobin drop of 3 to <5 g/dL or $\geq 10\%$ decrease in haematocrit • No observed blood loss: ≥ 4 g/dL decrease in the haemoglobin concentration or $\geq 12\%$ decrease in haematocrit • Any overt sign of hemorrhage that meets one of the following criteria and does not meet criteria for a major bleeding event: 
 ○ Requiring intervention (medical practitioner-guided medical or surgical treatment to stop or treat bleeding, including temporarily or permanently discontinuing or changing the dose of a medication or study drug) ○ Leading to or prolonging hospitalization ○ Prompting evaluation (leading to an unscheduled visit to a healthcare professional and diagnostic testing, either laboratory or imaging)
Minimal	
 • Any overt bleeding event that does not meet the criteria above • Any clinically overt sign of haemorrhage (including imaging) associated with a <3 g/dL decrease in haemoglobin concentration or <9% decrease in haematocrit
Bleeding in the setting of CABG	

 • Fatal bleeding (bleeding that directly results in death) • Perioperative intracranial bleeding • Reoperation after closure of the sternotomy incision for the purpose of controlling bleeding • Transfusion of ≥ 5 U PRBCs or whole blood within a 48-h period; cell saver transfusion will not be counted in calculations of blood products. • Chest tube output >2 L within a 24-h period 	

15.1.3 Global Utilization of Streptokinase and TPA for Occluded Arteries (GUSTO) definition of bleeding

Table 6 GUSTO Bleeding Definition (28)

Type	Definition
Severe or life-threatening	Intracerebral bleeding or bleeding resulting in substantial hemodynamic compromise requiring treatment
Moderate	Any bleeding not meeting the requirements for severe / life-threatening bleeding that requires transfusion
Minor	Other bleeding not requiring transfusion or causing hemodynamic compromise

15.1.4 International Society on Thrombosis and Haemostasis definition of bleeding

The ISTH classification of major bleeding in non-surgical patients includes any one of the following:

- Fatal bleeding,
- Symptomatic bleeding in a critical area or organ such as intracranial, intraspinal, intraocular, retroperitoneal, intra-articular or pericardial, or intramuscular with compartment syndrome,
- Bleeding causing a fall in haemoglobin level of 2 g/dL (1.24 mmol/L) or more, or leading to transfusion of two or more units of whole blood or red cells.(25)

15.2 Major Adverse Cardiovascular Events

Major adverse cardiovascular events (MACE) is the composite of cardiovascular death, non-fatal myocardial infarction, ischemic stroke, or clinically-driven revascularization. The definitions of the individual components of MACE are given below.

15.2.1 Death

All-cause death comprises several subclassifications (Table 7). In general, all deaths are considered cardiac unless an alternate cause is unequivocally established, even among subjects with serious noncardiac comorbidities.

Table 7 Classification of Death(29)

Cardiac death	Any death due to proximate cardiac cause (eg, MI, low-output failure, fatal arrhythmia), unwitnessed death and death of unknown cause, all procedure-related deaths including those related to concomitant treatment, will be classified as cardiac death.
Vascular death	Death caused by noncoronary vascular causes, such as cerebrovascular disease, pulmonary embolism, ruptured aortic aneurysm, dissecting aneurysm or other causes.
Noncardiovascular death	Any death not covered by the above definitions, such as death caused by infection, malignancy, sepsis, pulmonary causes, accident, suicide or trauma.

15.2.2 Myocardial Infarction

Myocardial infarction is defined according to the third universal definition(30) and includes:

- Type 1: spontaneous MI
- Type 2: MI secondary to an ischemic imbalance
- Type 3: MI resulting in death when biomarker values are unavailable
- Type 4a. MI related to PCI
- Type 4b: MI related to stent thrombosis

- Type 5: MI related to CABG

Any one of the following criteria meets the diagnosis of MI:

- Detection of a rise and/or fall of cardiac biomarker values (preferably cardiac troponin) with at least one value above the 99th percentile URL and with at least one of the following:
 - Symptoms of ischemia
 - (Presumed) new significant ST-T wave changes or new LBBB
 - Development of pathological Q waves
 - Imaging evidence of new loss of viable myocardium or new regional wall motion abnormality
 - Identification of an intracoronary thrombus by angiography or autopsy
- Cardiac death with symptoms suggestive of MI and presumed new ischemic ECG changes or new LBBB, but death occurred before cardiac biomarkers were obtained, or before cardiac biomarker values would be increased
- PCI related MI is arbitrarily defined by elevation of cardiac biomarkers
 - (>5 x 99th percentile URL) in patients with normal baseline values or
 - > 20% if the baseline values are elevated and are stable or falling

In addition, one of the following is required

- symptoms suggestive of ischemia
 - new ischemic ECG changes
 - angiographic findings consistent with a procedural complication OR
 - imaging demonstration of new loss of viable myocardium or new regional wall motion abnormality
- Stent thrombosis associated with MI when detected by coronary angiography or autopsy in the setting of myocardial ischemia and with a rise and/or fall of cardiac biomarker values with at least one value above the 99th percentile URL
 - CABG related MI is arbitrarily defined by elevation of cardiac biomarkers >10 x 99th percentile URL in patients with normal baseline values, AND one of the following:

- New pathological Q waves or new LBBB
- Angiographic documented new graft or new native coronary artery occlusion, or
- Imaging evidence of new loss of viable myocardium or new regional wall motion abnormality

15.2.3 Stroke

Stroke is defined as an acute symptomatic episode of neurological dysfunction, more than 24 hours in duration in the absence of therapeutic intervention or death, due to cerebral, spinal or retinal tissue injury as evidenced by neuroimaging or lumbar puncture. It includes the following subclassifications:

- Ischemic stroke: infarction due to prolonged ischemia. Causes include (but are not limited to) arterial and venous thrombosis, embolism, and systemic hypoperfusion.
- Hemorrhagic stroke: caused by a non-traumatic intraparenchymal, intraventricular or subarachnoid hemorrhage
- Undetermined: stroke with insufficient information to determine ischemic or hemorrhagic cause

Transient ischemic attack (TIA) is a transient episode of neurological dysfunction (< 24 hours) caused by temporary cerebral, spinal or retinal ischemia with no evidence of acute infarction on neuroimaging.

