11.1.3 Primary Ischemic Endpoint

The primary ischemic endpoint of the present study is the time to first occurrence of confirmed all-cause death, non-fatal myocardial infarction, or stroke.

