Analysis for the Primary Ischemic Endpoint: The analysis for the primary ischemic endpoint will be performed on the PP cohort. The primary objective is to determine if ticagrelor monotherapy is non-inferior to ticagrelor plus aspirin for the primary safety endpoint (all-cause death, non-fatal myocardial infarction, or stroke). A test of non-inferiority at the one-sided 0.025 level will be performed. Event rates will be estimated at one year and Kaplan-Meier curves will be plotted for the time from randomization to the first occurrence of confirmed all-cause death, non-fatal myocardial infarction, or stroke or by treatment group. Assuming an event rate of 8.0% in the control group, a sample size of 8200 will yield 80% to exclude a non-inferiority margin of 1.6%. If the upper limit of the 95% CI for the point estimate of the absolute risk difference is less than or equal to 1.6% then the criteria for non-inferiority will be met. This non-inferiority margin translates to a relative risk of 20% assuming the observed event rate equals 8.0% in the control arm.

Subgroup Analysis One year event rates for the primary efficacy and safety endpoints will be calculated in all subgroups described in section 12.2. Stratum-specific HRs and corresponding 95% CI will be calculated for each subgroup using a Cox proportional hazards

model. Formal interaction testing will be performed using the subgroup X treatment allocation as an additional term in the Cox model.

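### Under section 15.2.3 a survived, untreated episode of less than 24 hours with an acute infarct on imaging is neither stroke nor TIA, so it is not counted in the primary ischemic endpoint

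*Combined protocol and SAP*

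**What the plan says.** The stroke definition in section 15.2.3 (Appendix A) has a duration condition and a confirmation condition, both required. The episode must last "more than 24 hours in duration in the absence of therapeutic intervention or death" and must be "due to cerebral, spinal or retinal tissue injury as evidenced by neuroimaging or lumbar puncture". The same section defines TIA as an episode of under 24 hours "caused by temporary cerebral, spinal or retinal ischemia with no evidence of acute infarction on neuroimaging". Stroke has three subclasses: ischemic, hemorrhagic and a third worded as "Undetermined: stroke with insufficient information to determine ischemic or hemorrhagic cause".

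Stroke of any type is a component of the primary ischemic endpoint, which section 11.1.3 defines as "time to first occurrence of confirmed all-cause death, non-fatal myocardial infarction, or stroke". Section 12.2 judges that endpoint on the absolute risk difference with a margin of 1.6 percentage points: "A test of non-inferiority at the one-sided 0.025 level will be performed". Section 11.1.3 speaks of confirmed events and section 12.4 of adjudicated ones, but the documents contain no adjudication rule for stroke beyond 15.2.3. The data collection schedule in section 6.2 includes no neuroimaging.

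**The concern.** The stroke and TIA definitions should between them place every short ischemic episode, and they do not. The stroke definition sorts short episodes by duration; the TIA definition sorts them by duration and imaging. An episode that is short but imaging-positive fails both, so an adjudicator who follows the text has no class for it and records no endpoint event.

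There are two consequences. First, an objectively proven, symptomatic infarct is left out of the endpoint that decides non-inferiority. Section 1.3 names more thrombotic events as the risk of the placebo arm, so this is the kind of event the comparison is meant to detect. Second, because the 24-hour rule is relaxed for therapeutic intervention, two patients with the same infarct and the same symptom duration can be classed differently according to whether one was treated. Counting then depends partly on local care rather than on the event.

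**Working it through.** **Step 1. Cross the two definitions.** All criteria are from 15.2.3; the last column applies 11.1.3.

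| Episode | Stroke? | TIA? | In primary ischemic endpoint? |
|---|---|---|---|
| Under 24 h, no infarct on imaging, survived | No | Yes | No |
| Under 24 h, acute infarct, course altered by treatment | Can be | No | Can be |
| **Under 24 h, acute infarct, untreated, survived** | **No (duration)** | **No (infarct)** | **No** |
| Over 24 h, injury shown, type clear | Yes | No | Yes |
| Over 24 h, injury shown, type unclear | Yes (undetermined) | No | Yes |
| Over 24 h, no imaging or lumbar-puncture evidence, survived | No | No | No |
| Fatal, with or without imaging | – | – | Yes, as all-cause death |

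The third row is the gap. No other section closes it.

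**Step 2. The plan's own figure for this endpoint.** Sections 12.2 and 12.3 give 80% power with 8200 patients, an 8.0% event rate, a 1.6-point margin and one-sided 0.025. Assuming 1:1 allocation (4100 per arm; the text does not state the ratio):

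- SE = √(2 × 0.08 × 0.92 / 4100) = 0.00599
- Power = Φ(0.016 / 0.00599 − 1.96) = Φ(0.71) = 76.1%

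The stated 80% is not reproduced. That is a separate matter and does not bear on the definition.

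**Step 3. How many events might go uncounted.** The documents give no stroke rate and no share of short imaging-positive episodes, so both are assumed: a one-year stroke rate of 0.5% to 1.5%, with 10% to 30% of strokes failing the definition.

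- Low: 0.5% × 10% = 0.05 points; 4100 × 0.005 × 0.10 = 2 patients per arm
- High: 1.5% × 30% = 0.45 points; 4100 × 0.015 × 0.30 = 18 patients per arm

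The assumed share covers every unclassed non-fatal episode, including those over 24 hours without confirmation. The gap in the third row can account for no more than this.

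**Step 4. Effect on the difference between arms.** The margin applies to the difference, so only a difference in uncounted events matters. Equal losses in both arms move it by zero. If uncounted events carry a 20% relative excess under monotherapy (the relative size of the margin, 1.6 / 8.0), the hidden difference is:

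- 0.05 × 0.2 = 0.01 points, or 0.01 / 1.6 = 0.6% of the margin
- 0.45 × 0.2 = 0.09 points, or 0.09 / 1.6 = about 6% of the margin

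**Step 5. Effect on false non-inferiority.** Take a true difference of exactly 1.6 points (8.0% against 9.6%).

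- SE = √((0.08 × 0.92 + 0.096 × 0.904) / 4100) = 0.00625
- The chance of declaring non-inferiority with hidden excess d is Φ(d / SE − 1.96), with the SE recomputed for the counted rate
- d = 0: 2.5%; d = 0.01 points: about 2.6%; d = 0.09 points: about 3.5%

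If uncounted strokes were purely an excess in the monotherapy arm, hidden excesses of 0.1, 0.2 and 0.4 points would give 3.6%, 5.1% and 9.4%. Nothing in the documents supports so one-sided a pattern.

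**Step 6. Equal losses.** Removing 0.1 or 0.5 points from both arms lowers the counted control rate to 7.9% or 7.5%. The fixed margin then corresponds to a relative risk of 9.5 / 7.9 = 1.203 or 9.1 / 7.5 = 1.213, against 1.20 as planned. Power moves from 76.1% to 76.6% or 78.5%. Both changes are slight.

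**The case against.** The strongest reply is that the gap is narrow. The duration rule is relaxed for therapeutic intervention, and 15.2.3 does not limit which intervention qualifies, so many short infarcts may be admitted. Fatal strokes count as deaths in any case. What remains is the untreated survivor, and prior stroke is an exclusion (section 4.2). An adjudication charter, if one exists, might settle the matter. All of this limits the size of the problem. None of it supplies a class for the episode, and no charter text is in the documents.

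A reader might infer more than the text supports:

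- *That the undetermined class contradicts the definition.* It does not. That class concerns whether the cause is ischemic or hemorrhagic, not whether injury is proven, so proven injury of unclear cause fits it.
- *That episodes over 24 hours without imaging or lumbar-puncture proof are wrongly excluded.* Requiring objective proof is a legitimate choice of specificity for a confirmed endpoint, and the MI definition in 15.2.2 also rests largely on biomarker evidence. An early negative scan does not settle the case either, since 15.2.3 sets no imaging time and a later positive scan qualifies. A clinical-only route would trade missed events for misclassified ones, so it is not asked for here.
- *That 0.05 to 0.45 points of uncounted events per arm can be read against the 1.6-point margin.* The margin is on the between-arm difference, so that comparison is not valid.
- *That the definition by itself favours non-inferiority.* Fewer counted events follow from the text. A smaller difference follows only if the uncounted events are truly in excess in one arm.

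**Conclusion.** The gap is real and follows directly from the wording of 15.2.3: a non-fatal, untreated, imaging-proven infarct with symptoms under 24 hours has no class and is not counted in the primary ischemic endpoint, and treatment can change whether an identical infarct counts. Its effect on the non-inferiority result is probably small. Under an assumed 0.5% to 1.5% stroke rate, 10% to 30% of strokes uncounted, a 20% relative excess among them and 1:1 allocation, the difference shifts by at most about 0.1 point of the 1.6-point margin, and false non-inferiority goes from 2.5% to between about 2.6% and 3.5%. The stroke rate, the share and the excess are assumptions, not figures from the documents. The case for amending is that the rule is incomplete and cheap to repair, not that the trial's conclusion is at risk.

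**What to change.** Amend 15.2.3 and the adjudication form so that an acute symptomatic episode with imaging, lumbar-puncture or pathological evidence of acute infarction or hemorrhage is a stroke whatever its duration. Keep TIA as under 24 hours without infarct. The ischemic-stroke endpoints in 11.1.4 rely on the same definition and need no separate change; undetermined strokes should not be pooled with ischemic ones as part of this amendment.

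Apply the amended rule blinded to treatment and to all events, including those already adjudicated. The protocol is version 4.0 of March 2016 and section 9.3 estimates a start in February 2015, so some events may have been classed under the present wording.

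The cost is a sentence or two in Appendix A, a change to the form, and re-adjudication of a few earlier short episodes. No new tests or visits are needed.

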15.2.4 Stent thrombosis

Stent thrombosis is classified according to the level of certainty and timing following PCI(29) (Table 8).

- Definite stent thrombosis: is highly specific and requires angiographic or pathological confirmation of stent thrombosis in or within 5 mm of the stent in the setting of at least one of the following criteria with a 48-hour time window
 - Acute ischemic symptoms at rest
 - New ischemic ECG changes
 - Typical rise and fall in cardiac biomarkers
- Probable stent thrombosis includes
 - Any unexplained death within the first 30 days following PCI

- Any MI at any time following PCI that is related to documented acute ischemia in the territory of the implanted stent, in the absence of angiographic/pathological confirmation of stent thrombosis and no other obvious cause
- Possible stent thrombosis
 - Any unexplained death after the first 30 days following PCI until the end of trial follow-up

Table 8 **Timing of Stent Thrombosis**

Acute	0-24 hours following PCI
Subacute	>24 hours to 30 days following PCI
Late	>30 days to 1 year following PCI
Very late	>1 year following PCI

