5.2 Subject randomization and initiation of investigational product

5.2.1 Procedures for randomization

The eligibility for randomization for all enrolled subjects will be evaluated at the in-person 3-month study visit. Subjects with any of the following will not be randomized:

- Refusal of randomization by subject or treating physician
- Withdrawal of consent
- Lost to follow-up
- Death
- Major bleeding (BARC Types 3b or greater)
- Occurrence of an ischemic event after PCI such as myocardial infarction, definite or probable stent thrombosis, ischemic stroke, coronary revascularization with drug-eluting stent
- No longer taking DAPT with aspirin and ticagrelor
- Non physician-guided cessation of aspirin or ticagrelor of 5 consecutive days or greater.
- Women of child bearing potential (as defined in Section 4.2)
- Renal failure requiring dialysis
- Current indication for oral anticoagulation or high dose aspirin

Randomization will be performed within the EDC system among subjects eligible for randomization. The EDC will allocate the treatment group assignment for the subject and provide study site research personnel the appropriate bottle ID number(s).

Upon randomization at the conclusion of the in-person 3-month visit, the study site research personnel will provide a 6-month supply of blinded investigational product (aspirin or matching placebo) and open-label ticagrelor.

Enrolled subjects who do not meet eligibility for randomization will have completed their protocol required activities and therefore will not receive any further study-provided medications. Their treating physician will also be notified that the patient's protocol-mandated study activities have concluded. Further antiplatelet therapy will be at the discretion of the subject's treating physician in accordance with local standard of care. Vital status of these subjects will be determined at the 18-month time point.

Enrolled subjects who do not meet eligibility for randomization *prior to* the in-person 3-month visit will not be required to complete the 3-month in-person visit.

5.3 Procedures for handling subjects incorrectly enrolled or randomized on investigational product

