11.1.4 Secondary Ischemic Endpoints

Time to first occurrence of:

- cardiovascular death, non-fatal myocardial infarction, ischemic stroke or clinically-driven revascularization
- cardiovascular death, non-fatal myocardial infarction or ischemic stroke
- definite or probable stent thrombosis
- cardiovascular death
- non-fatal myocardial infarction
- cardiovascular death, non-fatal myocardial infarction or definite or probable stent thrombosis
- ischemic stroke
- all-cause mortality

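### Section 15.2.4 gives no class to a post-randomization death with stent thrombus proven at autopsy but no recorded symptom, ECG or biomarker criterion, so one secondary endpoint misses it

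*Combined protocol and SAP*

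**What the plan says.** Section 15.2.4 of the combined protocol and SAP grades stent thrombosis by how certain the diagnosis is, in three classes.

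- **Definite:** this class "requires angiographic or pathological confirmation of stent thrombosis in or within 5 mm of the stent in the setting of at least one of the" three clinical criteria listed there, within 48 hours. They are acute ischemic symptoms at rest, new ischemic ECG changes, and a typical biomarker rise and fall.
- **Probable:** either "Any unexplained death within the first 30 days following PCI", or an MI at any time after PCI that is tied to documented ischemia in the stented territory, "in the absence of angiographic/pathological confirmation of stent thrombosis and no other obvious cause".
- **Possible:** "Any unexplained death after the first 30 days following PCI until the end of trial follow-up".

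Section 11.1.4 lists time to first "definite or probable stent thrombosis" as a secondary ischemic endpoint in its own right. Possible cases are not in it. On timing, Section 5.2.1 states: "The eligibility for randomization for all enrolled subjects will be evaluated at the in-person 3-month study visit". The schedule in Section 6.2 puts that visit at day 90, plus or minus 14 days.

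**The concern.** The clinical condition follows the words for both kinds of confirmation and so governs both. Nothing exempts autopsy. That is workable for a living patient, who can report symptoms and have an ECG and biomarkers. It fails for a patient found dead, where the only evidence may be the thrombus seen at autopsy. The other two classes do not pick the case up, because each is worded for cases without such proof. In a scheme meant to rank by certainty, stronger evidence then gives a lower classification.

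Stent thrombosis is a named safety variable in Section 6.3, and Section 1.3 gives more thrombotic events in the placebo arm as a main risk of the trial. A count of definite or probable stent thrombosis that leaves out proven fatal cases is therefore incomplete where readers will look for harm.

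**Working it through.** No formula applies, and the plan has no figure to reproduce: it gives no stent thrombosis rate, and no sample size that depends on one. The check is to put one case through each rule.

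**Case.** A randomized patient is found dead at month 8. There are no witnessed symptoms, no ECG and no biomarkers. Autopsy shows thrombus in the stent.

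1. *Definite (15.2.4).* Pathological confirmation is present, but none of the three criteria is recorded. Not met.
2. *Probable, death route (15.2.4).* The death must be unexplained and within 30 days of PCI. The earliest scheduled randomization is day 90 − 14 = 76 after enrollment, which itself follows the index PCI, so every death after randomization is beyond 30 days from that procedure. The autopsy has also explained the death. Not met, on both counts.
3. *Probable, MI route (15.2.4).* This needs documented acute ischemia and the absence of pathological confirmation. Neither holds. Not met.
4. *Possible (15.2.4).* The death must be unexplained. Not met, and this class is outside the endpoint anyway.

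The case has no class. Under the censoring rule in Section 12.2 the patient is censored at death for this endpoint, although the death was the event.

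**Without the autopsy**, steps 1 to 3 still fail, but the death is unexplained and later than 30 days, so it is possible stent thrombosis.

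**Does the MI definition (15.2.2) rescue it?** No. Thrombus found at autopsy counts toward MI only with a biomarker rise or fall. The item on stent thrombosis with MI has the same biomarker requirement. The item for death before biomarkers needs both symptoms and presumed new ECG changes or left bundle branch block.

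**Where the death does count.** Section 15.2.1 classes unwitnessed deaths and deaths from a cardiac cause as cardiac. The patient is therefore an event for:
- the primary ischemic endpoint, as all-cause death (11.1.3);
- all-cause mortality and cardiovascular death (11.1.4);
- the three secondary composites that include cardiovascular death (11.1.4).

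**The case against.** The strongest reply is that the gap is narrow and touches nothing that decides the trial. That stands. The primary ischemic endpoint, its non-inferiority margin and the sample size do not change. A sudden death with a reported rest symptom, an ischemic ECG or a biomarker rise and fall within the window is still definite, so only deaths with none of the three recorded are lost.

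It may also be said that the definite class is meant to be specific, or that adjudicators would use common sense or the cited source. Specificity does not explain why positive pathology closes the probable route, or why a proven case ranks below an unproven one. Section 15.2.4 writes out its own rule, and nothing says that a citation overrides it.

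A reader might infer three stronger things that the documents do not support:

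- *That the arm with more fatal thromboses is made to look better.* The rule drops such cases in both arms of a double-blind trial. If a share f is lost in each, rates p1 and p2 become (1 − f)p1 and (1 − f)p2. The ratio is unchanged, the absolute difference shrinks by the factor (1 − f), and precision falls. A distorted ratio needs a different f by arm, and nothing in the documents shows that.
- *That the 30-day route can never apply after randomization.* Section 15.2.4 says PCI, not index PCI, and Section 5.8 foresees repeat procedures. An unexplained death soon after a repeat PCI could be probable. This does not help the autopsy case, which is explained.
- *That a number of lost events can be given.* The documents contain no stent thrombosis rate, autopsy rate or share of cases lacking all three criteria.

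**Conclusion.** The definition is wrong as written, with a limited effect. A post-randomization death with autopsy-proven stent thrombosis and none of the three clinical criteria recorded falls in no class and is missing from the stand-alone secondary endpoint of definite or probable stent thrombosis. The consequence is under-counting of proven fatal events in that endpoint, in both arms, by an amount that cannot be computed from the documents. The primary ischemic result, both mortality endpoints, the composites containing cardiovascular death and the sample size are untouched.

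The conclusion rests on reading Section 15.2.4 literally, and on treating a death as explained once autopsy shows the stent thrombus. If the second assumption were relaxed, the case would become possible and would still be outside the endpoint, unless the death fell within 30 days of a repeat PCI.

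**What to change.** Reword the definite class in Section 15.2.4 as two alternatives:

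- (a) angiographic confirmation with at least one of the listed clinical criteria within 48 hours; or
- (b) stent thrombosis confirmed at autopsy, in or within 5 mm of the stent, with no clinical criterion required.

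The change need go no further. Pathological confirmation in a living patient, such as from retrieved material, can stay under the present criteria, because no gap has been shown there.

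The cost is one line in Appendix A. It uses only autopsies already performed; Section 7.3.3 already records for serious adverse events whether one was done. No new data, visits or procedures are needed. The wording should be settled before such deaths are classified, so that one rule applies to all of them.
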